3.3 SELECTION OF TRIAL POPULATION

Approximately 700 patients will be screened for the trial in US. About 85 trial centres will be participating to ensure that approximately 154 patients are randomised to trial treatment (77 to each treatment group). The intention is that at least 2 patients should be randomised at each trial centre. Investigators who fail to screen at least one patient in the first 6 weeks of the trial may be re-evaluated for further participation. If enrolment is delayed, additional centres may be recruited.

Permission to randomise more than 8 patients per site must be obtained from the TCM at Boehringer Ingelheim. This will only be allowed after a careful review of the enrolment status.

Screening of patients for this trial is competitive, i.e. screening for the trial will stop at all centres when such a number of patients has been screened and it is anticipated that a

Proprietary confidential information.

© 2016 Boehringer Ingelheim International GmbH or one or more of its affiliated companies. All rights reserved.

This document may not - in full or in part - be passed on, reproduced, published or otherwise used without prior written permission.

sufficient number of patients will be randomised to trial treatment. Investigators will be notified when the appropriate number of patients has been screened and screening is complete, and will not be allowed to recruit additional patients for this study. Patients who have completed Visit 1 procedures prior to notification of the termination of recruitment will be allowed to continue in the study, if they meet all entry criteria and they are able to follow the visit schedule specified in this protocol.

The check for patient eligibility will be based upon a complete medical history including a physical examination and clinical laboratory tests. Judgement of the clinical relevance of a concomitant disease is at the discretion of the investigator. Conditions under therapy are always clinically relevant.

A log of all patients included into the study (i.e. having given informed consent) will be maintained in the ISF at the investigational site irrespective of whether they have been treated with investigational drug or not.

3.3.1 Main diagnosis for study entry

The study will be performed in black/African American patients (defined as a person having origins in any of the black racial groups of Africa as self-identified by the patient) with T2DM and hypertension that have insufficient glycaemic and BP control despite diet and exercise.

3.3.2 Inclusion criteria

1. Diagnosis of T2DM prior to informed consent.

Note: Documentation should be available before randomization at latest. Confirmation can be in the form of formal documents or by verbal communication of the date of diagnosis from a patient or from their primary care physician (if records are not available). It is up to the medical judgment of the Investigator to deem if the information is accurate.

2. Male and female black/African American patients on diet and exercise regimen who are EITHER

drug-naïve (defined as absence of any oral antidiabetic therapy, glucagon like peptide-1 (GLP-1) analog or insulin for 12 weeks, 16 weeks for pioglitazone prior to randomisation)

OR

pre-treated with stable dose of

- Metformin only, or
- Sulfonylurea only, or
- DPP-4 inhibitor only, or
- metformin plus sulfonylurea, or

Proprietary confidential information.

© 2016 Boehringer Ingelheim International GmbH or one or more of its affiliated companies. All rights reserved.

This document may not - in full or in part - be passed on, reproduced, published or otherwise used without prior written permission.

- metformin plus DPP-4 inhibitor.

Treatment has to be unchanged for a minimum of 12 weeks prior to randomization.

Dose for metformin: maximum tolerated dose

The maximum daily dose of SU or DPP-4 inhibitor should not exceed that stated in the local label.

3. HbA1c of $\geq 7.0\%$ (53 mmol/mol) and $\leq 11.0\%$ (97 mmol/mol) at Visit 1 (screening).
4. Mean seated SBP 140-180 mmHg at Visit 1 (screening).
5. Successful completion of baseline ABPM testing with a mean SBP 135-175 mmHg prior to randomisation.
6. Treatment with stable doses of at least one but not more than 4 antihypertensive medication ≥ 4 weeks prior to randomisation.
7. Age ≥ 18 years at Visit 1 (screening)
8. Signed and dated written informed consent by date of Visit 1 in accordance with Good Clinical Practice (GCP) and local legislation

3.3.3 Exclusion criteria

1. Uncontrolled hyperglycemia with a glucose level >270 mg/dl (>15.0 mmol/L) after an overnight fast during placebo run-in (includes Visit 2.1) and confirmed by a second measurement (not on the same day).
2. Exposure to any other antidiabetic medication within 12 weeks prior to randomisation other than metformin, sulfonylurea, DPP-4 inhibitor, metformin plus sulfonylurea or metformin plus DPP-4 inhibitor.
3. Current hypertension treatment with oral Minoxidil (topical minoxidil for hair growth is allowed).
4. Mean seated SBP ≥ 181 mmHg during placebo run-in visit and confirmed by a second measurement (not on the same day) preferably within one day.
5. Upper arm circumference that exceeds the upper circumference level of the cuff size of either ABPM and/or BP measurement device used in the study.
6. Night shift workers who routinely sleep during the daytime and/or whose work hours include midnight.
7. Diagnosis of autoimmune diabetes/Type I diabetes mellitus, monogenic (neonatal or maturity onset diabetes of the young (MODY)) diabetes or Type I diabetes in adults/latent autoimmune diabetes of adults (LADA) per investigator or patient medical history at the time of Visit 1 (screening).
8. Known or suspected secondary hypertension (e.g. renal artery stenosis, pheochromocytoma, Cushing's disease).

Proprietary confidential information.

© 2016 Boehringer Ingelheim International GmbH or one or more of its affiliated companies. All rights reserved.

This document may not - in full or in part - be passed on, reproduced, published or otherwise used without prior written permission.

9. History or evidence of hypertensive retinopathy (Keith-Wagener grade III or IV) and/or hypertensive encephalopathy.
10. Clinically significant valvular heart disease or severe aortic stenosis in the opinion of the investigator.
11. Acute coronary syndrome (non- ST wave elevated myocardial infarction (STEMI), STEMI and unstable angina pectoris), stroke or transient ischemic attack within 3 months prior to informed consent.
12. Indication of liver disease, defined by serum levels of either ALT (SGPT), AST (SGOT), or alkaline phosphatase above 3 x upper limit of normal (ULN) as determined during screening and/or run-in phase.
13. Impaired renal function, defined as eGFR < 45 ml/min/1.73m² (moderate renal impairment, chronic kidney disease epidemiology collaboration CKD-EPI formula) as determined during screening and/or run-in phase.
14. Bariatric surgery within the past two years and other gastrointestinal surgeries that induce chronic malabsorption.
15. Medical history of cancer (except for basal cell carcinoma) and/or treatment for cancer within the last 5 years.
16. Blood dyscrasias or any disorders causing hemolysis or unstable Red Blood Cells (e.g. malaria, babesiosis, haemolytic anaemia, thalassemia, sickle cell anaemia (sickle cell trait is allowed)).
17. Medical history and signs and symptoms of diabetic autonomic neuropathy.
18. Treatment with anti-obesity drugs 3 months prior to randomisation (i.e. surgery, aggressive diet regimen, etc.) leading to unstable body weight.
19. Current treatment with systemic steroids at time of informed consent or change in dosage of thyroid hormones within 6 weeks prior to informed consent or any other uncontrolled endocrine disorder except T2DM in the opinion of the investigator.
20. Pre-menopausal women (last menstruation ≤ 1 year prior to informed consent) who:
 - are nursing or pregnant or
 - are of child-bearing potential and are not practicing an acceptable method of birth control, or do not plan to continue using this method throughout the study and do not agree to submit to periodic pregnancy testing during participation in the trial. Acceptable methods of birth control include tubal ligation, transdermal patch, intra uterine devices/systems (IUDs/IUSs), oral, implantable or injectable contraceptives, complete sexual abstinence (if acceptable by local authorities), double barrier method and vasectomised partner.
21. Alcohol, drug or confectionary liquorice abuse within the 3 months prior to informed consent that would interfere with trial participation or any ongoing condition leading to a decreased compliance to study procedures or study drug intake in the investigator's opinion.

Proprietary confidential information.

© 2016 Boehringer Ingelheim International GmbH or one or more of its affiliated companies. All rights reserved.

This document may not - in full or in part - be passed on, reproduced, published or otherwise used without prior written permission.

22. Intake of an investigational drug in another trial within 30 days prior to intake of study medication in this trial; or participating in another trial (involving an investigational drug and/or follow-up) after discontinuing medication in that trial.
23. Any other clinical condition that would jeopardize patient's safety while participating in this clinical trial in the opinion of the investigator.

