3.3.5 Re-screening

Re-screening is permitted for the following categories of screen failed patients only:

- Patients who were screen failed due to exclusionary background anti-diabetic therapies (sulfonylurea, DPP4-inhibitor, metformin + sulfonylurea, metformin +DPP4-inhibitor) according to prior versions of the protocol.
- Patients who were screen failed due to exclusionary HbA1c 7.0% (53 mmol/mol) - 7.4% (57 mmol/mol) at Visit 1 according to prior versions of the protocol. Patients

Proprietary confidential information.

© 2016 Boehringer Ingelheim International GmbH or one or more of its affiliated companies. All rights reserved.

This document may not - in full or in part - be passed on, reproduced, published or otherwise used without prior written permission.

who were screen failed due to exclusionary HbA1c below 7.0% or above 11.0% cannot be re-screened.

- Patients who were screen failed due to exclusionary mean seated DBP (Visit 1) according to prior versions of the protocol. However, mean seated SBP (Visit 1) must have been 140-180 mmHg at the previous screening.
- Patients who were screen failed due to taking 4 antihypertensive medications (≥ 4 weeks prior to randomization) according to prior versions of the protocol.
- Patients who were screen failed due to out-of-window visits prior to ABPM testing (Visit 2.2). If ABPM testing has commenced, no re-screening is permitted.

A patient who was screen failed due to any of the above screen failure reasons is permitted to be re-screened once only. A new patient number should be assigned to the re-screened patient who should be re-consented. Rationale for re-screening must be document in source documents.

Re-screening is not permitted for patients who were screen failed due to other reasons.

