4.2.1 Rescue medication, emergency procedures, and additional treatments

Throughout the duration of the trial, patients should continue to take their current therapy, the dose of which should remain unchanged if at all possible (for further details see below). This medication will not be provided as part of the clinical trial supplies, unless required by local laws and regulations.

Rescue medication, for the treatment of hyperglycemia, can be initiated during the double-blind treatment period of the trial (i.e. from Visits 3-7.2) and during follow up period but only if the criteria below are met:

- Week 1 – 12 (i.e. up to and including the result from Visit 5.2):
The patient has a glucose level > 270 mg/dl (> 15.0 mmol/l) after an overnight fast
- Week >12 – 26 (i.e. from the day after Visit 5.2 onwards):
The patient has a glucose level > 200 mg/dl (> 11.1 mmol/l) after an overnight fast

Proprietary confidential information.

© 2016 Boehringer Ingelheim International GmbH or one or more of its affiliated companies. All rights reserved.

This document may not - in full or in part - be passed on, reproduced, published or otherwise used without prior written permission.

The above results should be confirmed, meaning that there is a minimum of two measurements, at least one of which should be performed after an overnight fast at the investigational site, and on a different day to the initial (overnight fast) measurement.

A FPG and an HbA1c sample should be taken before initiation of rescue therapy and sent to central lab for analysis. The HbA1c sample is not required if a sample has been taken and sent to the central lab for analysis within the last 4 weeks.

Special attention must be paid to monitor for instances of DKA. All patients must be made aware of this potential risk and need to be instructed to contact the Investigator or other healthcare professional in case of symptoms of DKA. For further details see [Section 2.3](#).

In case of a suspected DKA the Investigator should ensure that appropriate tests are performed at the earliest opportunity according to local guidelines, such as a blood gas test (i.e. pH, bicarbonate; the results will be collected on the relevant page of the eCRF) and that the patient is appropriately treated (i.e. hospitalized or referred to emergency treatment) according to local treatment guidelines.

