Rescue medication, for the treatment of hypertension, can be initiated during the double-blind treatment period of the trial (i.e. from Visits 3-7.2) and during follow up period but only if the criteria below are met:

- Week 1 – 4 (i.e. up to and including the result from Visit 4.0):
The patient has a mean seated SBP level ≥ 180 mm Hg and/or mean seated DBP level ≥ 110 mm Hg at the clinic visit
- Week 4 – 26 (i.e. from the day after Visit 4.0 onwards):
The patient has a mean seated SBP level ≥ 160 mm Hg and/or mean seated DBP level ≥ 100 mm Hg at the clinic visit

The above results should be confirmed, meaning that there is a minimum of two seated blood pressure measurements (second measurement at the investigational site on a different day to the initial measurement).

If the above criteria are met, the initiation of rescue medication is at the Investigator's discretion, based on the patient's current clinical condition (e.g. ongoing illness etc.). The choice of rescue medication will depend upon the current medication. Adjustment of the current therapy or addition of another antidiabetic and/or antihypertensive medication would be appropriate. Rescue medication and its dosage will be left to the discretion of the Investigator and the administration of rescue medication is to be conducted according to GCP with the exception of the following:

- Due to their known effect on blood pressure, thiazolidinediones (eg pioglitazone) and GLP-1 analogs must not be used as rescue medication for hyperglycemia.
- Any SGLT-2 inhibitor that is or may become available during the conduct of this trial must not be used as rescue medication.

Proprietary confidential information.

© 2016 Boehringer Ingelheim International GmbH or one or more of its affiliated companies. All rights reserved.

This document may not - in full or in part - be passed on, reproduced, published or otherwise used without prior written permission.

Regardless of the choice made, rescue medication should be taken in accordance with the local prescribing information of that respective medication, taking into account potential contraindications. Rescue medication can be used from when it is initiated until the end of the trial.

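### Entry criteria set no upper diastolic limit, so a patient already at the week 1-4 rescue level for seated DBP can be randomised (minor patient-safety point)

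*Protocol*

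**What the plan says.** Three entry criteria in the protocol refer to a blood pressure value:

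- Section 3.3.2, criterion 4: "Mean seated SBP 140-180 mmHg at Visit 1 (screening".
- Section 3.3.2, criterion 5: "Successful completion of baseline ABPM testing with a mean SBP 135-175 mmHg prior to randomisation".
- Section 3.3.3, criterion 4: "Mean seated SBP ≥ 181 mmHg during placebo run-in visit and confirmed by a second measurement", on a different day.

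None gives a diastolic value. SAP section 6.2, code G2.21, notes that the run-in criterion is systolic only from Protocol Version 4.

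Protocol section 4.2.1 allows hypertension rescue from Visit 3. Up to Visit 4 the level is "mean seated SBP level ≥ 180 mm Hg and/or mean seated DBP level ≥ 110 mm Hg"; after that it is 160/100 mmHg. Either must be confirmed at the site on a different day, and starting rescue is left to the investigator.

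**The concern.** A trial normally sets its entry ceiling so that nobody is randomised at a level the protocol itself regards as needing rescue. For diastolic pressure there is no ceiling, so a patient can start blinded treatment at or above the rescue level. Half of the patients receive placebo, added to antihypertensive therapy that is meant to stay unchanged.

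Run-in offers no way out under the protocol. Hypertension rescue does not start before Visit 3. Section 4.2.2.1 bars other antihypertensive agents outside rescue, and inclusion criterion 6 requires stable doses for at least 4 weeks before randomisation. For a high run-in DBP, the only thing between the patient and randomisation is the investigator's opinion. After Visit 3, the flow chart's next scheduled vital signs are at Visit 4 (day 29).

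**Working it through.** The plan states no figure on this point, so the check is a comparison of thresholds. Seated means are rounded to whole mmHg (protocol Appendix 10.2).

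| Measure | Highest value that may enter | First-stage rescue | Overlap |
|---|---|---|---|
| Fasting glucose | 270 mg/dl (excluded above this, confirmed) | above 270 mg/dl | none |
| Seated SBP | 180 mmHg (excluded at a confirmed 181) | 180 mmHg or more | the single value 180 |
| Seated DBP | no limit | 110 mmHg or more | 110 and above, with no upper end |

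The glucose row rests on criterion 1 of section 3.3.3, "Uncontrolled hyperglycemia with a glucose level >270 mg/dl (>15.0 mmol/L) after an overnight fast during placebo run-in", and on the rescue rule for weeks 1-12, "The patient has a glucose level > 270 mg/dl (> 15.0 mmol/l) after an overnight fast". Those two limits match. The systolic limits match to within 1 mmHg. Only the diastolic row is open.

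Take a hypothetical patient with seated 160/112 mmHg on two run-in days and a 24-hour ambulatory mean SBP of 150 mmHg:

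1. Visit 1 criterion: with the same 160 mmHg at screening, 140 ≤ 160 ≤ 180, met.
2. Ambulatory criterion: 135 ≤ 150 ≤ 175, met.
3. Run-in exclusion: 160 < 181, not triggered.
4. Week 1-4 rescue level: 112 ≥ 110, reached on the diastolic arm.

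On blood pressure the patient is eligible. If DBP stays at that level, rescue criteria are met once it is measured from Visit 3 and confirmed on another day.

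**Other criteria.** Exclusion 8 (secondary hypertension), exclusion 9 (grade III or IV retinopathy, or encephalopathy) and exclusion 23 (any condition judged unsafe by the investigator) may stop some such patients. None is a diastolic limit.

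**Stated reason.** Section 11.3, cited only for the sponsor's reasoning, says the Visit 1 DBP range was removed to admit isolated systolic hypertension. The run-in DBP ceiling was removed to align with that change. Isolated systolic hypertension means a low or normal DBP with a high SBP, so admitting it needs the lower bound removed. It gives no reason to remove the upper one.

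**Size.** The documents contain no DBP distribution, so the affected fraction p cannot be derived. The expected number is 154 × p. As a scale only, p = 1% would be 154 × 0.01 = 1.5 patients.

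**The case against.** **SBP was the chosen severity limit.** Section 11.3 says patients with severe hypertension remain excluded by the upper SBP limit. That sentence justifies allowing a fourth antihypertensive drug, not removing DBP, and an SBP limit does not exclude a patient at 160/112.

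**Entry near a rescue level is part of the design.** Patients enter with inadequate control. SBP up to 180 is allowed, while rescue falls to 160/100 after Visit 4 and the glucose limit falls to 200 mg/dl after week 12. This stands for the later, stricter steps, which should be left alone. It does not explain why first-stage limits match for glucose, nearly match for SBP, and are absent for DBP.

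**Safeguards exist.** Eligibility is reviewed again at Visit 3, exclusion 23 applies, and rescue is available from that visit. This stands and keeps the point minor.

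**Inferences to avoid.** A reader might go further in four ways that the documents do not support:

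- *Section 2.3 is contradicted.* It describes patients as stable with regard to BP control for at least 4 weeks. That fits the stable-dose criterion; it does not claim blood pressure at goal.
- *The re-screening rule is a separate inconsistency.* Section 3.3.5 re-admits "Patients who were screen failed due to exclusionary mean seated DBP (Visit 1) according to prior versions of the protocol", with a condition on SBP only, while keeping both outer HbA1c limits. It simply follows the current criteria: HbA1c has limits and DBP has none.
- *The gap specifically damages the week-12 ambulatory endpoints.* A patient whose antihypertensive therapy changes before the Visit 5.1 recording would have no on-treatment ambulatory value to carry forward (SAP sections 6.6.2.4 and 7.5.1). That is true of any early change, whatever its cause.
- *SAP code G1.11 wrongly removes isolated systolic patients from the per-protocol set.* Its description still names DBP 90-110 mmHg, but its criterion entry is missing from the available text. Codes A2.01, G1.12 and G2.21 carry Version 4 notes, so G1.11 may too.

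**Conclusion.** The gap is real and follows directly from the text: no entry criterion has an upper diastolic limit, and first-stage rescue applies at a confirmed seated DBP of 110 mmHg. It is a minor patient-safety point and a cheap improvement. It is not a flaw in the efficacy analysis.

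Its size is unknown. That it is probably small is a judgement: a patient must have DBP of 110 mmHg or more on two run-in days with SBP no higher than 180, while taking one to four antihypertensive drugs. Any percentage, or any probability that at least one such patient is randomised, would depend on an assumed DBP distribution, so none is given as a result.

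**What to change.** 1. In protocol section 3.3.3, criterion 4, exclude a mean seated SBP of 181 mmHg or more and/or a mean seated DBP of 110 mmHg or more during run-in, confirmed on a different day. Set no lower DBP limit, so that isolated systolic hypertension stays eligible. Section 3.3.5 needs no change, because re-screened patients would meet the new limit in run-in.
2. In SAP section 6.2, update code G2.21 to match, for patients entered under the amended version.

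Separately, the sponsor could check that G1.11 carries a Version 4 note. No edit is proposed on the text available.

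The 110 mmHg limit matches first-stage rescue. The former run-in ceiling of 111 mmHg (section 11.3) would close nearly all of the gap, leaving the same 1 mmHg overlap as SBP.

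The cost is one amendment with ethics approval, one SAP edit and a few extra screen failures, number unknown. Seated pressure is already taken on two run-in days, at Visit 2.1 and after the ambulatory monitor is removed at Visit 2.2. If confirmation within one day is wanted, as the current SBP criterion prefers, a few patients would need a repeat reading.
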